17.3 Clinical Laboratory Evaluation

The following safety laboratory parameters are measured

Hematology

- White blood cell (WBC) count
- Lymphocytes (absolute count, %)
- Monocytes (absolute count, %)

Sprifermin (AS902330) Statistical Analysis Plan (Final) EMR700692 006-v1.0

- Neutrophils (absolute count, %)
- Eosinophils (absolute count, %)
- Basophils (absolute count, %)
- Red blood cells
- Hematocrit
- Hemoglobin
- Platelets

Clinical biochemistry

- Aspartate aminotransferase (AST)
- Alanine aminotransferase (ALT)
- Alkaline phosphatase (ALP)
- Total protein
- Total bilirubin
- Creatine kinase (CK)
- Creatinine
- Calcium
- Phospate
- Sodium
- Potassium
- Magnesium
- Urea (Blood urea nitrogen (BUN))
- Glucose (not fasting)
- Chloride
- Albumin
- High-sensitivity C-reactive protein (hsCRP)
- Erythrocyte sedimentation rate (ESR)

Urinalysis

- Dipstick parameters
- pH
- Specific gravity

Sprifermin (AS902330) Statistical Analysis Plan (Final) EMR700692 006-v1.0

- Protein
- Glucose
- Ketones
- Bilirubin
- Blood
- Urobilinogen
- Leukocytes

Antibodies to sprifermin /FGF-18 (if data available)

- Binding antibodies
- Neutralizing antibodies

Coagulation parameters

- Partial thromboplastin time (PTT)
- International Normalized Ratio (INR)

Pregnancy test: Serum during screening, urine at other visits

Hematology, clinical biochemistry and urinalysis parameters and their corresponding change from baseline variables will be summarized by parameter, treatment and timepoint.

Analysis of antibodies to sprifermin will be provided by Merck Serono QPD and presented by number of observations (n), number of missing values (missing), and the count and percentage of subjects with positive findings of antibodies by treatment and time point, and will be included in the Safety Section of the CTR accordingly as specified in Section 16.3. In case of too low numbers of anti-FGF18 antibodies only a listing will be generated.

Reference ranges from the central laboratory will be used to define Lower limit of normal (LLN) and Upper limit of normal (ULN). For the purposes of laboratory parameter summaries, 'low', 'normal' and 'high' are classified as follows: low < LLN; LLN \le normal \le ULN; high > ULN.

A shift table will be used to summarize for each laboratory parameter the number and percentage of subjects experiencing low, normal, high or missing values at each timepoint according to their baseline classification, by treatment group.

Mean values of continuous parameters will be plotted per timepoint and corresponding change from baseline. One symbol per treatment group will be used. Plots will also present reference range limits. Plots will be split by gender whenever reference limits are gender-dependent.

Scatter plots of the following continuous parameters will be provided for the 2 years analysis (up to LOCF1):

• baseline vs largest post-baseline value

• baseline vs lowest post-baseline value

Plots will include 95% CI around the mean and present reference range limits.

Coagulation and pregnancy parameters collected during screening only will be listed.

Laboratory values that are outside the normal range will also be flagged in the data listings, along with corresponding normal ranges. Baseline is the last measurement prior to the first dose of any trial treatment. Subjects without post baseline laboratory samples will be excluded from analyses with respect to values after the baseline.

In addition, the last available laboratory measurement (LOCF1 for 2 years analysis and LOCF2 for 5 years analysis) will be presented.

17.4 Vital Signs

The following vital signs will be summarized by treatment and timepoint together with absolute change from baseline in the same manner specified for laboratory parameters. All analysis are for timepoints defined in table 3a and 3b.

- sitting systolic and diastolic blood pressure
- heart rate
- body temperature

All parameters will be listed by subject and visit, including all relevant criteria (as specified below) and flags.

The maximum changes of blood pressure measurements from baseline to maximum shifts (with pre-specified categories for increase and decrease separately) after start of 1st injection will be summarized (number of subjects and percentages) and grouped by baseline category as follows (missing values will be defined as a separate category):

Table 8 Blood pressure categories

Baseline category	Post-baseline category
Systolic baseline: < 140 mmHg, ≥ 140 mmHg	Increase of: ≤20 mmHg, > 20-40 mmHg, > 40 mmHg
Systolic baseline: < 140 mmHg, ≥ 140 mmHg	Decrease of: ≤20 mmHg, > 20-40 mmHg, > 40 mmHg
Diastolic baseline: ≤ 90 mmHg, >90 mmHg	Increase of: ≤10 mmHg, > 10-20 mmHg, > 20 mmHg

Diastolic baseline: ≤ 90 mmHg, > 90 mmHg	Decrease of: ≤10 mmHg, > 10-20 mmHg, > 20 mmHg
	20 mmHg

For each subject both the worst increase and worst decrease during the 2 year period (after first injection) will be used. If subject has no change (change=0), then it will not be counted in the categories of increase and decrease. The following summaries will be prepared for blood pressure as grouped above only for subjects who have post baseline values:

• Maximal shifts (change in categories [increase and decrease]), this will be done both relative to injections and relative to target days following either table 3a or table 3b.

Mean values will be plotted per timepoint. One symbol per treatment group will be used.

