- Visit 7 must be conducted within 21 to 27 weeks of the actual date of Visit 4,
- Visit 12 must be conducted within 21 to 27 weeks of the actual date of Visit 9, and
- Visit 17 must be conducted within 21 to 27 weeks of the actual date of Visit 14

Allowable intervals for other visits:

During the DBPC treatment phase, visits may take place within ± 4 days of the planned day. This interval allowance applies to Visits 5, 6, 10, 11, 15, 16, 20, and 21.

Extended follow-up visits may take place within ± 21 days of the planned day. This interval allowance applies from Visit 22 (EF1) through Visit 28 (EF6).

Allowable intervals for X-rays and MRIs:

At time points where IMP administration is scheduled, X-rays and MRIs may be performed up to 3 days before the IMP administration.

During the DBPC phase, at time points where there is no IMP administration scheduled, X-rays and MRIs may be performed within ± 4 days of the planned day.

During the extended follow up phase, at time points when there is no IMP administration scheduled, X-rays and MRIs may be performed within ± 7 days of the planned day.

Pain Medication Washout

Subjects will be requested to discontinue the intake of all pain medications for 5 half-lives before a visit involving completion of the WOMAC. At least 3 days before each such visit, subjects will be contacted by phone to remind them of this requirement.

Aspirin (acetylsalicylic acid) used for cardiovascular protection does not need to be withheld, nor do antidepressants used for management of OA pain or depression.

Subject Questionnaires

At visits involving completion of subject questionnaires (WOMAC, PGA, KOOS QOL, KOOS Symptom Index, PGIC, NRS pain score in the target and contralateral knee, MOS SF-36, pain in other joints, and ICOAP), these questionnaires must be completed before any other trial procedures are performed. The WOMAC should be completed first.

Subject Diaries

Subjects will receive diaries at each visit for recording of the following information:

- Any adverse reaction occurring between trial visits and any concomitant medications used, with particular attention to the use of NSAIDs, coxibs, and any other pain medications
- Maximum pain level (using a 100-mm VAS) and presence or absence of joint swelling, to be recorded once daily on the day before each IMP injection and on each of the 3 days following an IMP injection.

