Surgical procedures (target knee)	Continuous																	
Review of subject diaries	X	X	X	X	X	X	X	X	X	X	X	X	X	X	X	X	X	X
Vital signs ⁽²⁾	X	X	X	X	X	X	X	X	X	X	X	X	X	X	X	X	X	X
Physical examination ⁽³⁾	X				X	X				X	X	X	X	X	X	X	X	
ECG	X										X							
Clinical laboratory specimens ⁽⁴⁾	X					X					X	X	X	X	X	X	X	
Antibodies to sprifermin/FGF-18	X			X		X			X		X							
PK serum collection ⁽⁵⁾			X					X			X							
Biomarker serum collection ⁽⁶⁾			X					X			X							
Biomarker urine collection			X					X			X							
PGt sample collection ⁽⁷⁾	One sample is needed. It can be taken at any trial visit.																	
Pregnancy test (urine) ⁽⁸⁾	X					X					X		X		X		X	
20-meter walk test	X				X	X				X	X	X	X	X	X	X	X	
Knee X-ray ⁽⁹⁾⁽¹⁰⁾	X										X		X		X		X	
Target Knee MRI ⁽¹⁰⁾	X					X					X		X		X		X	
Synovial fluid collection ⁽¹¹⁾	X	X	X			X	X	X										
i.a. injection of IMP	X	X	X			X	X	X										

Table footnotes appear on following page.

Abbreviations: AEs: adverse events; ECG: electrocardiogram; i.a: intra-articular; ICOAP: Measure of Intermittent and Constant Osteoarthritis Pain; KOOS: Knee Injury and Osteoarthritis Outcome Score; MRI: magnetic resonance imaging; NRS: numerical rating scale; PGIC: Patient Global Impression of Change; PK: pharmacokinetic; QOL: quality of life; WOMAC: Western Ontario and McMaster Universities Osteoarthritis Index
ET: Early Termination (procedures shown for this visit should be performed at the time of early treatment discontinuation or trial withdrawal.) EF: Extended follow-up.

Subjects will be requested to discontinue the intake of any pain medications for at least 5 half-lives before a visit involving completion of the WOMAC.

At visits where IMP is administered, all procedures should be performed before dosing unless otherwise specified. Subject questionnaires (WOMAC, PGA, KOOS QOL, KOOS Symptom Index, PGIC, NRS in both knees, pain in other joints, MOS SF-36, and ICOAP) should be completed before any other procedures are performed; the WOMAC should be completed first.

At each visit, subjects will be given trial diaries which will be collected and reviewed at the following visit (see Section 7.1.1).

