^{*}treatment cycle; Day 1 is first treatment day. If multiple assessments are available within each study week window, the one closest to target day will be used. At Baseline, week 26, 52 and 78 [injections visits] pre injection assessments will be considered for the corresponding study week window). & for X-ray and this timepoint with injections - only compare to first injection in cycle # 3. don't compare to first injection in cycle #2 to determine if used in analysis or not. ~For SF36, lab, height, weight (and BMI), and pain in other joint, in the 2-years period, assessments are scheduled as qMRI, so qMRI windowing will be used. For the 2-5 years the scheduling is like ADQS, therefore, ADQS windowing will be used for these assessments.

For vital signs, which are measured at all visits, two mappings will be used, one relative to injections and one relative to target days.

Table 3a Vital signs relative to injections

Study week window	To be used relative to injection visit independent of ADY	AVISITN for injection - related ADVS
Cycle 1/Week 0/pre-injection assessment/Baseline	Yes	1
Cycle 1/Week 1/pre-injection assessment	Yes	2
Cycle 1/Week 2/pre-injection assessment	Yes	3
Cycle 1/Week 3	Yes	4
Cycle 2/Week 0/pre-injection assessment	Yes	5
Cycle 2/Week 1/pre-injection assessment	Yes	6
Cycle 2/Week 2/pre-injection assessment	Yes	7
Cycle 2/Week 3	Yes	8
Cycle 3/Week 0/pre-injection assessment	Yes	9
Cycle 3/Week 1/pre-injection assessment	Yes	10
Cycle 3/Week 2/pre-injection assessment	Yes	11
Cycle 3/Week 3	Yes	12
Cycle 4/Week 0/pre-injection assessment	Yes	13
Cycle 4/Week 1/pre-injection assessment	Yes	14
Cycle 4/Week 2/pre-injection assessment	Yes	15
Cycle 4/Week 3	Yes	16

Table 3b Vital signs relative to target days

Study week window	ADVS target day (min, max)	AVISITN for relative visit ADVS
Baseline	1 (-42, 1)	1
Month 3/Week 12	85 (2, 133)	2
Month 6/Week 26	183 (134, 224)	3
Month 9/Week 38	267 (225, 315)	4
Month 12/Week 52	365 (316, 406)	5
Month 15/Week 64	449 (407, 497)	6
Month 18/Week 78	547 (498, 588)	7
Month 21/Week 90	631 (589, 679)	8
Month 24/Week 104	729 (638, 819)	9
Month 30/Week 130	911 (820, 1001)	10
Month 36/Week 156	1093 (1002, 1183)	11
Month 42/Week 182	1275 (1184, 1365)	12
Month 48/Week 208	1457 (1366, 1547)	13
Month 54/Week 234	1639 (1548, 1729)	14
Month 60/Week 260	1821 (1730, 1849)	15
LOCF1 (up to Month 24)	Last post-baseline measurement	
	in DBPC (2, 819)	20

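### In SAP Table 3b the Week 90 and Week 104 vital-sign windows share days 638 to 679, and no rule says which visit takes a reading in that range

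*SAP*

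**What the plan says.** SAP Section 11 sets the analysis-visit windows. For vital signs it states: "For vital signs, which are measured at all visits, two mappings will be used, one relative to injections and one relative to target days". The injection-based mapping is in Table 3a and the target-day mapping is in Table 3b. Section 17.4 applies both: "All analysis are for timepoints defined in table 3a and 3b".

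Table 3b lists Week 90 as target day 631, window (589, 679), and Week 104 as target day 729, window (638, 819). In the questionnaire column of Table 3, Week 90 has the same window but Week 104 is (680, 819).

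The only selection rule is in the footnote to Table 3: "If multiple assessments are available within each study week window, the one closest to target day will be used". It chooses among readings inside one window. It does not choose between two windows that hold the same reading.

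The protocol allows readings on off-schedule days. In Appendix E the Week 104 visit doubles as the early-termination visit, and its "procedures shown for this visit should be performed at the time of early treatment discontinuation or trial withdrawal".

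**The concern.** A visit-window table should send each study day to one visit. Here 42 days go to two, and two tables in the same SAP section disagree on where Week 104 begins. Programmers following the text could reach different Week 90 and Week 104 counts.

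Change in vital signs is a named safety endpoint. The SAP keeps carried-forward values in a separate row of Table 3b (LOCF1, the last post-baseline value up to day 819). A withdrawal reading placed in the Week 104 row blurs that separation, because a value taken well before two years then appears as an observed two-year value.

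**Working it through.** **Inputs.** Windows and target days: SAP Section 11, Tables 3 and 3b. Visit tolerances: Protocol Section 7.1.1. Dropout of 30% and 545 subjects: Protocol Section 8.1, repeated in SAP Section 7.

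**1. Reproduce the table's own figures.** Target day = 7 × week + 1. Week 90: 7 × 90 + 1 = 631. Week 104: 7 × 104 + 1 = 729. Both agree.

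Every other post-baseline window in Table 3b starts on the day after the previous one ends (for example 588/589 and 819/820). On that pattern Week 104 starts at 679 + 1 = 680, as in Table 3, and not at 638.

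The figure 638 can be reached another way: 729 − 91 = 638 and 729 + 90 = 819. That is the shape of the Week 130 row (911 − 91 = 820, 911 + 90 = 1001). It looks like a half-year window set without regard to the Week 90 row.

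**2. Overlap.** 679 − 638 + 1 = 42 days. The midpoint of the two targets is (631 + 729)/2 = 680, so all 42 days are nearer to the Week 90 target. They lie 729 − 679 = 50 to 729 − 638 = 91 days before the Week 104 target, or about 7 to 13 weeks.

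**3. Who can have a reading there.** For Week 90 the protocol states: "During the DBPC treatment phase, visits may take place within ± 4 days of the planned day". That gives days 627 to 635. Visit 22 is allowed ±21 days, which gives days 708 to 750. No in-tolerance Week 90 or Week 104 visit falls in the overlap. Readings there come from withdrawals, late Week 90 visits or unscheduled visits. The last planned injection is at Week 80 (7 × 80 + 1 = day 561), so on schedule there is no treatment left to stop by day 638.

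**4. Closest-to-target rule, applied window by window.**

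| Reading days | Week 90 row (either table) | Week 104 row, lower bound 680 | Week 104 row, lower bound 638 |
|---|---|---|---|
| 631 and 729 | 631 | 729 | 729 |
| 631 and 650 | 631 | empty | 650 |
| 645 only | 645 | empty | 645 |
| 645 and 729 | 645 | 729 | 729 |

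The second line is the usual withdrawal: Week 90 attended, then a leaving visit. The leaving reading fills Week 104 and nothing is used twice. Double use appears only in the third line.

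**5. Number of subjects.** Assume dropout is even over 729 days and every leaver has a reading: 0.30 × 42/729 × 545 = 9.4, about 9 subjects, or 9.4/545 = 1.7%. Both assumptions are mine. The second makes this an upper figure, because Protocol Section 7.1.5 asks for withdrawal assessments only where possible.

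**The case against.** The strongest reply is that the consequence is minor. Protocol Section 8.5.4 and SAP Section 19.1 make vital signs descriptive, and the key safety tables in SAP Section 19.5.3 do not include them. Wide early bounds are also the SAP's own practice: Table 3 opens the two-year window at day 589 for quantitative MRI and day 407 for X-ray. Even with a lower bound of 680, a withdrawal reading on day 680 (49 days early) still counts as Week 104. All of this stands and limits the point to a small one. It does not remove the overlap. Those wide windows adjoin their neighbours, so each day still has one visit.

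Four stronger readings are tempting, and the documents do not support them.

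- **Every subject leaving in the overlap is counted twice.** Such a subject would normally have a Week 90 reading on days 627 to 635, which is closer to day 631 than any reading from day 638 on.
- **The overlap displaces true Week 104 readings.** The nearest overlap day is 50 days from target, so the true reading would have to fall on day 780 or later. The tolerance ends at day 750.
- **The SAP prescribes duplication.** It does not. It leaves the assignment of a shared day open.
- **The blood-pressure shift tables are distorted.** The SAP says that "this will be done both relative to injections and relative to target days following either table 3a or table 3b", but each subject contributes one worst increase and one worst decrease over the two years. Placing a reading in two rows cannot change these.

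**Conclusion.** The point holds as a defect in one table cell. Table 3b assigns days 638 to 679 to both Week 90 and Week 104, Table 3 does not, and nothing in the SAP settles which visit takes a shared reading.

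The practical result is that some withdrawal readings, 50 to 91 days early and closer to Week 90, can be shown as observed Week 104 data. On the two assumptions above this is at most about 9 of 545 subjects. Use of one reading in both rows is an edge case: it needs a missed or very late Week 90 visit and no closer Week 104 reading up to day 819.

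Only the by-visit summaries and plots built on Table 3b are affected. Table 3a and the efficacy analyses are untouched. The documents give no vital-sign values from which a shift in means could be computed. With so few readings involved, it should be small.

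**What to change.** In Table 3b, change the Week 104 window from (638, 819) to (680, 819), matching the questionnaire column of Table 3. The overlap becomes zero and each reading maps to one visit. A lone reading on day 645 then counts as Week 90 only. A leaving reading on day 650 after an attended Week 90 visit remains available as the LOCF1 value.

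If the half-year width was intended for vital signs, the SAP should say so and add a rule that gives each shared day to one visit.

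The cost is one number in the SAP and the matching line of the dataset specification. No new data are needed and no other analysis changes.

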17.5 Physical Examination

Weight, height, and BMI will be summarized by treatment and timepoint as will absolute change from baseline.

17.6 ECG Evaluation

Standard 12-lead ECGs (reporting ventricular rate/HR, PR, QRS, QT, and QTc intervals) will be summarized by treatment and timepoint as will absolute change from baseline. Presentation of QTc intervals will also include the Bazett's and Fridericia's correction defined as

Bazett's Correction (QTcB)
$$QTc_b = \frac{QT}{\sqrt{RR}}$$

Fridericia's Correction (QTcF)
$$QTc_f = \frac{QT}{\sqrt[3]{RR}}$$

where: RR = RR-interval measured in seconds (RR = 1/HR).

Mean values of continuous parameters will be plotted per analysis timepoint. One symbol per treatment group will be used. All ECG parameters will be listed by subject and visit.

18 References

References available upon request.

- 2. Independent Data Monitoring Committee Charter version 2, July 2014.
- 3. Attur, M. et al. Radiographic severity of knee osteoarthritis is conditional on interleukin 1 receptor antagonist gene variations. Annals of Rheumatic Diseases. 2010; 69, 856–861.
- 4. Wu X et al. IL-1 receptor antagonist gene as a predictive biomarker of progression of knee osteoarthritis in a population cohort. Osteoarthritis and Cartilage 2013; 21, 930–938.
- 5. Siebuhr et al., Identification and characterization of osteoarthritis patients with inflammation derived tissue turnover. Osteoarthritis and Cartilage 2014; (22) 44-50.
- 6. Sharif et al., A 5-yr longitudinal study of type IIA collagen synthesis and total type II collagen degradation in patients with knee osteoarthritis- association with disease progression. Rheumatology 2007;46: 938–943.
- 7. Kraus et al., Application of biomarkers in the development of drugs intended for the treatment of osteoarthritis: Osteoarthritis and Cartilage 2011; (19) 515-542.
- 8. Gudmann et al., Cartilage turnover reflected by metabolic processing of type II Collagen: A novel marker of anabolic function in chondrocytes. International Journal of Molecular Sciences. 2014; 15:18789-18803.
- 9. Pham T, van der Heijde D, Altman RD, Anderson JJ, Bellamy N, Hochberg M, et al. OMERACT-OARSI initiative: Osteoarthritis Research Society International set of responder criteria for osteoarthritis clinical trials revisited. Osteoarthritis Cartilage 2004; 12:389-99.

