7.4.4 Vital Signs, Physical Examinations, and Other Assessments

Physical examinations and measurement of height, weight, and vital signs (sitting systolic and diastolic blood pressure, heart rate, and body temperature) will be performed at the time points specified in [Appendix E](#).

Standard 12-lead ECGs (reporting ventricular rate, PR, QRS, QT, and QTc intervals) will be obtained at the time points specified in [Appendix E](#). ECGs will be read centrally; procedures for transfer of data to the central reader are provided in the MOP. Original 12-lead ECG tracings will be retained in each individual subject's medical file. In case of abnormal results, a second original will be provided to the Sponsor. ECGs can be repeated at the discretion of the Investigator or co-Investigator.

One of the trial's safety endpoints is the incidence of AIRs, defined as increase of pain by 30 mm on a 100-mm VAS and a self-reported synovial fluid effusion (i.e., joint swelling) within 3 days following i.a. injection (see Section 7.4.1.1). Subjects will use trial diaries to record maximum levels of target knee pain experienced, using a 100-mm VAS, and presence or absence of joint swelling in the target knee. Completed diaries will be collected and reviewed at each visit, and information will be transcribed to the CRFs following medical review. AIRs will be identified by the Sponsor based on the information about pain and swelling transcribed from the diaries to the CRFs.

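### SAP 17.6 asks for RR in seconds but converts it as 1/HR, which inflates derived QTcB and QTcF if heart rate is in beats per minute and the line is programmed literally

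*SAP*

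**What the plan says.** Protocol Section 7.4.4 lists what the ECG delivers: "Standard 12-lead ECGs (reporting ventricular rate, PR, QRS, QT, and QTc intervals) will be obtained at the time points specified in" the schedule in Appendix E, with central reading. SAP Section 17.6 repeats the list: "Standard 12-lead ECGs (reporting ventricular rate/HR, PR, QRS, QT, and QTc intervals) will be summarized by treatment and timepoint", and adds absolute change from baseline, mean plots and by-subject listings. It then brings in two derived quantities: "Presentation of QTc intervals will also include the Bazett's and Fridericia's correction defined as" QTcB = QT divided by the square root of RR, and QTcF = QT divided by the cube root of RR. The definition of RR under those formulas is "where: RR = RR-interval measured in seconds (RR = 1/HR".

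Three things are absent from both documents. No unit is given for heart rate or ventricular rate, either in the ECG sections or where heart rate appears among the vital signs (Protocol 7.4.4, SAP 17.4). RR is not among the ECG parameters listed as reported. No factor of 60 or other conversion appears, and SAP Section 9, which lists changes and clarifications, does not touch the point.

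**The concern.** A rate in beats per minute inverts to minutes per beat, so RR in seconds is 60/HR. The SAP fixes the unit of RR as seconds, leaves the unit of HR open, and supplies a conversion that fails for the unit in which ventricular rate is usually expressed. Because RR is not listed as a reported variable, someone working from the documents has to derive it from HR, and the bracket is the only derivation offered.

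Change in 12-lead ECG parameters is a named safety endpoint (Protocol 8.3.3; SAP Section 6). If the bracket were coded as it stands with HR in beats per minute, the QTcB and QTcF levels, their absolute changes from baseline, the mean plots and the listings would all carry the error.

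**Working it through.** **Inputs.** From SAP 17.6: QTcB = QT / RR^(1/2), QTcF = QT / RR^(1/3), RR in seconds, RR = 1/HR. Assumed, because the documents give no unit: HR in beats per minute. A QT of 400 ms and the heart rates below are illustrative and are not trial data.

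**Does the stated conversion hold?** It depends on the unit of HR.

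- HR in beats per second: 1/HR is in seconds. At 75 beats per minute, HR = 75/60 = 1.25 per second and RR = 1/1.25 = 0.8 s. The SAP line holds and there is no error.
- HR in beats per minute: 1/HR = 1/75 = 0.01333, which is RR in minutes. In seconds it should be 60/75 = 0.8. The stated value is too small by a factor of 60.

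**Size of the error under beats per minute.** RR enters as a divisor under a root, so an RR that is 60 times too small multiplies the result by a constant:

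- QTcB: 60^(1/2) = 7.746
- QTcF: 60^(1/3) = 3.915

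Direct evaluation with QT = 400 ms:

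| HR (beats/min) | RR = 60/HR (s) | QTcB, 60/HR | QTcB, 1/HR | QTcF, 60/HR | QTcF, 1/HR |
|---|---|---|---|---|---|
| 50 | 1.2 | 365.1 | 2828.4 | 376.4 | 1473.6 |
| 60 | 1.0 | 400.0 | 3098.4 | 400.0 | 1565.9 |
| 75 | 0.8 | 447.2 | 3464.1 | 430.9 | 1686.9 |
| 100 | 0.6 | 516.4 | 4000.0 | 474.3 | 1856.6 |

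The ratio is the same in every row: 7.746 for QTcB and 3.915 for QTcF.

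**Changes from baseline.** Each value is multiplied by the same constant c, so the absolute change becomes c × post − c × baseline = c × (post − baseline). A true 10 ms change would appear as 10 × 7.746 = 77 ms for QTcB or 10 × 3.915 = 39 ms for QTcF. In a percent change the constant cancels, but SAP 17.6 asks for absolute change.

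**The case against.** The strongest reply is that the governing definition is sound. The SAP says RR is measured in seconds, both correction formulas are right for that, and the bracket can be read as a reminder that RR and rate are reciprocals. On this view the fault is a missing unit, and harm follows only if a programmer puts beats per minute into the bracket and ignores the word seconds. That is correct about the condition, and it limits the finding. It does not make the line right: the bracket is the only route to RR that the documents provide, and it fails for the usual unit.

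Several further points stand and bear on importance.

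- Literal use would give values of roughly 1500 to 4000 ms, which would be conspicuous in the listings and plots that Section 17.6 requires.
- The two corrections are presented in addition to the QTc reported with the ECG. That QTc does not pass through the bracket and offers an order-of-magnitude check.
- SAP Appendix 19.1 classes ECG as descriptive in both phases. Section 17.6 sets no QTc threshold, outlier category or test, and ECG is absent from the key tables, figures and listings in Appendix 19.5.
- QT and ventricular rate are recorded, so corrected values can be recomputed without loss of data.

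A reader might infer more: that every Bazett and Fridericia value this trial produces will be wrong, that the trial has no valid QTc, or that the dataset specification contains the same mistake. The documents support none of these. The first needs both the unit assumption and literal programming. The second overlooks the reported QTc. The third concerns a specification that is not among the documents and may already use 60/HR or a measured RR.

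**Conclusion.** The conversion in SAP 17.6 is wrong for heart rate in beats per minute and right only for beats per second. If HR is in beats per minute and the line is coded as written, derived QTcB and QTcF, and their absolute changes from baseline, are inflated by 7.75 and 3.91 at every heart rate.

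The conclusion rests on two conditions that the documents do not settle: the unit of HR, and whether the bracket is programmed literally. The confidence attaches to the wording of the SAP and to the two factors. Whether any output would carry the error cannot be told from the documents. The reported QTc, percent changes, the primary analysis, the sample size and the efficacy endpoints are unaffected. This is a minor but real error in the operative text for a descriptive safety summary.

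**What to change.** In SAP 17.6, replace the bracket with: RR (seconds) = 60/HR, with HR the ECG ventricular rate in beats per minute. Alternatively, if the central reader supplies a measured RR interval in seconds, say that this value is used and delete the conversion. Then check that the programming specification agrees with whichever is chosen.

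The cost is one line in the SAP and a check of the specification. Design, data collection and all other analyses stay as they are.
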